1.4. Summary of Known Risks and Benefits to Human Subjects

The anticipated clinical benefit of the study lenses will be the correction of refractive error. No adverse device effects are anticipated. The risks associated with use of the study lenses are considered to be the same as those for other marketed soft contact lenses worn in the same modality (i.e., daily disposable wear), and these risks are considered acceptable relative to the clinical benefits. Comprehensive risk and benefit information regarding the study lenses is included in the AO1D and AO1DfA package inserts (Appendix C).

Clinical Study Protocol

Johnson & Johnson Vision Care, Inc.

1.5. Relevant Literature References and Prior Clinical Data Relevant to Proposed Clinical Study

The AO1D and AO1DfA lenses are FDA-approved and have been marketed commercially since 2016 and 2017, respectively. For further details regarding prior clinical data, refer to the AO1D and AO1DfA package inserts (Appendix C).

2. STUDY OBJECTIVES, ENDPOINTS AND HYPOTHESES

2.1. Objectives

Primary Objective

The primary objective of this study is to evaluate the difference in High-Luminance, High-Contrast (HLHC) Visual Acuity (VA) between binocular correction with AO1DfA and AO1D contact lenses in habitual contact lens wearers with low astigmatism.

Secondary Objectives

The secondary objectives of this study are to assess the CLUE subjective vision score and subject overall preference for AO1DfA and AO1D contact lenses in habitual contact lens wearers with low astigmatism. HLHC VA will also be assessed with subjects wearing their own habitual spectacle correction and compared to that with the AO1DfA lens.

2.2. Endpoints

Primary endpoint

The primary endpoint will be the HLHC VA for the contact lens wear periods.

HLHC VA will be assessed using ETDRS charts under controlled lighting conditions, which will be monitored and verified each testing day (room illumination greater than 400 lux, and chart luminance between 120 and 200 cd/m²). VA will be scored letter-by-letter in logMAR units.

Secondary Endpoints

Secondary endpoints for this study will be the subject overall preference between sphere (AO1D) and toric (AO1DfA) correction at the final study visit, the CLUE vision score at 1-week follow-up for each contact lens correction (AO1D, AO1DfA) at follow-up, and the HLHC VA with spectacle correction.

Subjective quality of vision will be assessed using Contact Lens User Experience (CLUE) questionnaire. CLUE is a patient-reported outcomes questionnaire to assess patient-experience attributes of soft, disposable contact lenses (comfort, vision, handling, and packaging) in a contact-lens wearing population in the US, ages 18-65. Derived CLUE scores using Item Response Theory (IRT) follow a normal distribution with a population average score of 60 (SD 20), where higher scores indicate a more favorable/positive response.⁸ A 5-point increase in an average CLUE score translates into 10% shift in the distribution of scores for population of soft disposable contact lens wearers.

Clinical Study Protocol

Johnson & Johnson Vision Care, Inc.

Overall preference between AO1D and AO1DfA correction will be assessed using a preference questionnaire at the final visit. The questionnaire will include 'no overall preference' option.

Other Exploratory Endpoints

Exploratory endpoints for this study will be:

Other observations (efficacy):

- High-Luminance, Low-Contrast (HLLC) VA at follow-up, and with spectacle wear at the end of the washout period
- Number of diagnostic lenses required to achieve fit success for the contact lens corrections
- Length of time required to fit the contact lens corrections
- CLUE comfort and handling scores at 1-week follow-up for the contact lens corrections, and CLUE vision with spectacle wear at the end of the washout period
- MRD and NEI-RQL questionnaire response for the contact lens corrections and with spectacle wear at the end of the washout period
- Subjective ranking of corrections (sphere, toric, and habitual spectacles) in order of preference at the final visit
- Average wear time and comfortable wear time for the contact lens corrections
- Lens fitting characteristics for the contact lens corrections
- Settled lens orientation (for the AO1DfA contact lenses only)
- Subject reported ocular symptoms

Other observations (safety):

- Slit lamp findings
- Adverse events

2.3. Hypotheses

Primary Hypothesis

1. After 1 week of wear, monocular HLHC VA for correction with AO1DfA lenses will be superior to that for mean sphere correction with AO1D spherical lenses.

Secondary Hypotheses

1. After 1 week of wear, the mean CLUE vision score for binocular correction with AO1DfA lenses will be superior to that for binocular mean sphere correction with AO1D spherical lenses.
2. After 1 week of wear HLHC VA for correction with AO1DfA lenses will be non-inferior to that for correction with subjects' habitual spectacles, using a non-inferiority boundary of -0.05 logMAR.
3. After 1 week of wear, subjects will have greater overall preference for binocular correction with AO1DfA lenses over AO1D spherical lenses.

The primary hypothesis must be met for the study to be considered successful.

Clinical Study Protocol

Johnson & Johnson Vision Care, Inc.

3. TARGETED STUDY POPULATION

3.1. General Characteristics

The target population for this study will be adult soft contact lens wearers between 18 and 39 years of age (inclusive) with myopia and low astigmatism (suitable for correction with either -0.75 or -1.25 cylinder power) in both eyes. Note that the target population may habitually wear sphere or toric lenses, so long as they meet the refractive eligibility criteria.

3.2. Inclusion Criteria

Potential subjects must satisfy of all the following criteria to be enrolled in the study.

Inclusion Criteria following Screening

The subject must:

1. Read, understand, and sign the STATEMENT OF INFORMED CONSENT and receive a fully executed copy of the form.
2. Appear able and willing to adhere to the instructions set forth in this clinical protocol.
3. Be between 18 and 39 (inclusive) years of age at the time of screening.
4. By self-report, habitually wear soft contact lenses (sphere or toric) in both eyes in a daily reusable or daily disposable wear modality (i.e. not extended wear modality). Habitual wear is defined as a minimum of 6 hours of wear per day, for a minimum of 2 days per week during the past 4 weeks.
5. Possess a wearable pair of spectacles that provide correction for distance vision.

Inclusion Criteria at Baseline Evaluation

The subject must:

6. In both eyes, have magnitude of the cylinder component of their vertex-corrected distance refraction greater than or equal to 0.625 DC and less than 1.625 DC.
7. In both eyes, have the mean sphere of their vertex-corrected distance refraction minus half of the indicated contact lens label cylinder power be between -0.875 to -4.625 DS (inclusive).
8. For each eye, have the cylinder axis of their distance refraction between 165° and 15° (i.e., 180±15°, inclusive) or between 75° and 105° (i.e., 90±15°, inclusive).
9. For both eyes, have the sphere power of their habitual spectacles within ±0.50 Diopters Sphere (DS) (inclusive) of the sphere power of their current subjective refraction.
10. For both eyes, have the cylinder power of their habitual spectacles within ±0.50 Diopters Cylinder (DC) (inclusive) of the cylinder power of their current subjective refraction.
11. For both eyes, have the cylinder axis of their habitual spectacles within ±20° (inclusive) of the cylinder axis of their current subjective refraction.
12. Achieve monocular VA of 20/30 or better with their habitual spectacles in both eyes.

Clinical Study Protocol

Johnson & Johnson Vision Care, Inc.

3.3. Exclusion Criteria

Potential subjects who meet any of the following criteria will be excluded from participating in the study:

Exclusion Criteria following Screening

The subject must not:

1. Be currently pregnant or lactating.
2. Be diabetic.
3. Be currently using any ocular medications or have any ocular infection of any type.
4. By self-report, have any ocular or systemic disease, allergies, infection, or use of medication that might contraindicate or interfere with contact lens wear, or otherwise compromise study endpoints, including infectious disease (e.g., hepatitis, tuberculosis), contagious immunosuppressive disease (e.g., Human Immunodeficiency Virus [HIV]), autoimmune disease (e.g. rheumatoid arthritis, Sjögren's syndrome), or history of serious mental illness or seizures. See section 9.1 for additional details regarding excluded systemic medications.
5. Have habitually worn rigid gas permeable (RGP) lenses, orthokeratology lenses, or hybrid lenses (e.g. SynergEyes, SoftPerm) within the past 6 months.
6. Be currently wearing monovision or multifocal contact lenses.
7. Be currently wearing lenses in an extended wear modality.
8. Have a history of strabismus or amblyopia.
9. Be an employee (e.g., Investigator, Coordinator, Technician) or immediate family member of an employee (including partner, child, parent, grandparent, grandchild or sibling of the employee or their spouse) of the clinical site.
10. Have participated in a contact lens or lens care product clinical trial within 7 days prior to study enrollment.

Exclusion Criteria at Baseline Evaluation

The subject must not:

11. Have clinically significant (grade 3 or higher on the FDA grading scale) slit lamp findings (e.g., corneal edema, neovascularization or staining, tarsal abnormalities or bulbar injection) or other corneal or ocular disease or abnormalities that contraindicate contact lens wear or may otherwise compromise study endpoints (including entropion, ectropion, chalazia, recurrent styes, glaucoma, history of recurrent corneal erosions, aphakia, moderate or above corneal distortion, herpetic keratitis).
12. Have fluctuations in vision due to clinically significant dry eye or other ocular conditions.
13. Have had or have planned (within the study period) any ocular or intraocular surgery (e.g., radial keratotomy, PRK, LASIK, iridotomy, retinal laser photocoagulation, etc.).

3.4. Enrollment Strategy

Study subjects will be recruited from the Institution/clinical site's subject database and/or utilizing Independent Ethics Committee (IEC) or Institutional Review Board (IRB) approved materials.

Clinical Study Protocol

Johnson & Johnson Vision Care, Inc.

4. STUDY DESIGN AND RATIONALE

4.1. Description of Study Design

This will be a 5-visit, randomized, partially single-masked, bilateral wear, dispensing, 2-treatment \times 2-period crossover study with spectacle-wear washout and wash-in periods. Subjects will be randomized into one of two unique sequences to wear each contact lens correction one at a time (sphere followed by toric or toric followed by sphere). For each of the two wear periods, lenses will be worn bilaterally in a daily wear, daily disposable modality for 7(\pm 2) days. Lenses will be worn for a minimum of 8 hours per day on at least 5 days of the wear period. There will be a 7(\pm 2) day wash-in period prior to the first study lens wear period, and a 7(\pm 2) day washout period between the first and second wear periods. During the wash-in and washout periods, subjects will only wear their own habitual spectacle correction (i.e., no contact lens wear). Subjective comfort, vision, and handling will be assessed at fitting and follow-up visits for each contact lens wear period using the CLUE questionnaire, and CLUE vision will also be assessed at the end of the washout period. HLHC VA and HLLC VA will be assessed with the study contact lenses at the 1-week follow-up visits and with spectacle wear at the end of the washout period. At the final study visit, contact lens preference will be assessed (i.e., preference between the study contact lenses) as well as overall correction ranking (i.e., corrections ranked by preference considering both study lenses and habitual spectacles). Subjects will not have access to the study lenses following completion of the protocol.

4.2. Study Design Rationale

A crossover design was chosen for efficient comparison of the two study lenses with a relatively small sample size, as this removes inter-subject variance from the comparison. Washout and wash-in periods with equal duration to the wear periods are included to reduce the potential for carryover effects and to allow comparison with the subject's habitual spectacle correction.

The AO1D and AO1DfA lenses were chosen as they have the same base material, and both have a history of commercial success. The CLUE questionnaire was selected on the basis of being the best available validated PRO tool for assessing subjective overall comfort, vision and handling among the population of soft contact lens wearers. HLHC VA using ETDRS charts was included on the basis of this being the best available method for objectively assessing visual acuity.

The investigational lenses will be fitted by optometrists who are experienced at fitting soft contact lenses and will be evaluated by habitual contact lens wearers in their standard wearing environment.

4.3. Enrollment Target and Study Duration

This study will have an enrollment target of 170 subjects, with a target of at least 153 to complete. The study will be conducted at approximately 12 clinical sites, where the enrollment target for each site will be approximately 14 subjects. A subject will be considered enrolled upon signing of the informed consent form.

Clinical Study Protocol

Johnson & Johnson Vision Care, Inc.

There will be 5 visits in total per subject; total study duration including the enrollment period is expected to be approximately 11 weeks. Subjects who are discontinued prior to the final evaluation may be replaced at the discretion of the study sponsor. The investigation will end at the time that the study data is hard locked.

5. TEST ARTICLE ALLOCATION AND MASKING

5.1. Test Article Allocation

This will be a randomized, partially subject-masked, 2×2 crossover study. Subjects will be randomized into one of 2 unique sequence groups in a 1:1 allocation ratio to wear 2 different study lenses one at a time bilaterally over 2 wear periods (AO1D followed by AO1DfA, or AO1DfA followed by AO1D).

Use of the test articles will be randomized using a randomization scheme supplied by the study biostatistician. The randomized assignment of subjects will be performed at the first visit prior to the first fitting. Clinical sites will follow the randomization scheme provided and will not pre-select or assign subjects. The following must have occurred prior to randomization:

- Informed consent must have been obtained
- The subject must have met all inclusion and exclusion criteria
- The subject history and baseline information must have been collected

Randomly-permuted block randomization will be used to avoid bias in the assignment of subjects to treatment and to enhance the validity of statistical comparisons across treatment groups.

When dispensing test articles, the following steps should be followed to maintain randomization codes:

1. Investigator or designee (documented on the Delegation Log) will consult the randomization scheme (lens fitting schedule) to obtain the test article assignment for that subject prior to dispensing.
2. Investigator or designee will record the subject's number on the appropriate line of the randomization scheme (lens fitting schedule).
3. Investigator or designee will pull the appropriate test articles from the study supply. All test articles that are opened, whether dispensed (placed/fit on eye or dispensed outside the clinical site) or not, must be recorded on the Test Article Accountability Log in the "Dispensed" section.

5.2. Masking

This will be a partially single-masked trial; subjects will not be aware of the identity (i.e., brand) of the assigned lenses, however, they will be able to differentiate between the AO1D and AO1DfA lenses due to differences in label powers, lens shape and scribe markings. Due to the different fitting procedure requirements for sphere and toric lenses, investigators and site staff will not be masked.

Clinical Study Protocol

Johnson & Johnson Vision Care, Inc.

5.3. Procedures for Maintaining and Breaking the Masking

Two randomization codes (alphanumeric characters) will be generated, one for the AO1D lens and one for the AO1DfA lens, using the form [REDACTED]. Study lenses will be supplied in blister packs labelled with the study number, lot number, sphere power, expiration date and the randomization codes. Sponsor personnel involved in the conduct of the trial will not be masked to the identity of study lenses.

When dispensing test articles, the following steps should be followed to maintain randomization codes:

1. Investigator or designee (documented on the Delegation Log) will consult the lens fitting schedule to obtain the test article assignment for that subject prior to dispensing.
2. Investigator or designee will record the subject's number on the appropriate line of the lens fitting schedule.
3. Investigator or designee will pull the appropriate test articles from the study supply. All test articles that are opened, whether dispensed (placed/fit on eye or dispensed outside the clinical site) or not, must be recorded on the Test Article Accountability Log in the "Dispensed" section.

Under normal circumstances, the mask should not be broken until all subjects have completed the study and the database is finalized. Otherwise, the mask should be broken only if specific emergency treatment/course of action would be dictated by the subject knowing their treatment status. In the event the mask is broken, the sponsor must be informed as soon as possible. The date, time, and reason for the unmasking must be documented in the subject record.

Subjects who have had their treatment assignment unmasked are expected to return for all remaining scheduled evaluations. If necessary, subjects who are discontinued may be replaced to reach the subject completion target.

6. STUDY INTERVENTION

6.1. Identity of Test Articles

Parameters for the test and control designs to be used in this study are shown in the table below:

Clinical Study Protocol

Johnson & Johnson Vision Care, Inc.

Table 1: Test and Control Article Parameters

	AO1DfA	AO1D
Test Article Form	Soft contact lens	
Design / Description	ACUVUE® OASYS 1-Day with HydraLuxe® Technology for Astigmatism	ACUVUE® OASYS 1-Day with HydraLuxe® Technology
Manufacturer	Johnson & Johnson Vision Care, Inc.	
Packaging Form	Blister packaging in sterile packing solution	
Packaging Solution	Optimized Borate Buffer (OBB) solution	
Lens Material	senofilcon A	
Sphere Powers (DS)	-1.00 to -4.50 in 0.25 steps	-1.25 through -5.50 (inclusive) in 0.25 steps
Cylinder Powers (DC)	-0.75, -1.25	N/A
Cylinder Axes (°)	10, 80, 90, 100, 170, 180	N/A
Fiducial marks	6 and 12 o'clock fiducial lines	N/A
Nominal Water Content (%)	38	
Nominal Base Curve (mm)	8.5	
Lens Diameter (mm)	14.3	
Dk (Fatt method, boundary corrected, edge corrected, $\times 10^{-11}$ [cm ² /sec] [ml O ₂ /ml \times mm Hg] at 35°C)	103	
Modality in Current Study	Daily wear	
Replacement Frequency in Current Study	Daily disposable	

For the AO1DfA lens, the total number of test lenses to be used (not including lenses that are replaced due to droppage, loss or damage) is expected to be approximately 2380 lenses (target enrollment of 170 subjects \times 2 eyes per subject \times 7 days per wear period). Test and control lenses will be worn in an even ratio, thus the total number of lenses to be used (including both test and control) is expected to be approximately 2380 lenses.

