2.6	Lens selection	
Assign the study lens based on the randomization scheme. Select the fitting lens powers based on vertex-corrected subjective refraction for each eye, with consideration of the following guidelines.
 
For toric lenses:
 
 1. Label cylinder axis should be determined by rounding the refraction cylinder axis to the nearest 10 degrees. Axis ending in the digit '5' should be rounded towards 180 for eyes with with-the-rule astigmatism, or towards 90 for eyes with against-the-rule astigmatism (e.g. 175 should be rounded to 180, 105 should be rounded to 100). 2. Cylinder power should be chosen based on the following table: 
 
 Vertex corrected cylinder power (X) within the range: (DC)	Label cylinder power to be fit (DC)	
 
 $-0.625 \leq X < -1.125$	-0.75	
 
 $-1.125 \leq X < -1.625$	-1.25	
 
 
 3. The fitting lens spherical equivalent (SE) power (label sphere power + 1/2 of the label cylinder power) should be as close as possible to the SE of the vertex-corrected refraction. If the SE of the vertex- 	Vertex corrected cylinder power (X) within the range: (DC)	Label cylinder power to be fit (DC)	$-0.625 \leq X < -1.125$	-0.75	$-1.125 \leq X < -1.625$	-1.25	
Vertex corrected cylinder power (X) within the range: (DC)	Label cylinder power to be fit (DC)								
$-0.625 \leq X < -1.125$	-0.75								
$-1.125 \leq X < -1.625$	-1.25								

Clinical Study Protocol
Johnson & Johnson Vision Care, Inc.

Visit 2: Lens Fitting #1		
Step	Procedure	Details

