2.11	General lens fit assessment	
The fitting characteristics of the lens in both eyes will be assessed using a slit lamp. Lens position (centration, limbal exposure, edge lift) and movement (primary and up gaze as well as push-up) will be assessed. Fit acceptability is defined as any lens that does not display the following general fit characteristics:
 
 • Limbal exposure (presence of clear cornea) in any direction of gaze. • Edge lift • Insufficient movement in all three movement assessments (primary gaze, up-gaze and push-up test). • Excessive movement in primary gaze 
If the general fit is unacceptable for either eye, the subject will be discontinued (proceed to exit evaluation).

Clinical Study Protocol
Johnson & Johnson Vision Care, Inc.

Visit 2: Lens Fitting #1		
Step	Procedure	Details
2.12	Spherical over-refraction	
Perform monocular spherical over-refraction. Where possible, use the duo-chrome test to refine the endpoint as described in step 1.11 (the final spherical endpoint may be determined binocularly).
 
The spherical over-refraction must be plano in both eyes to continue.
 
If a non-plano over-refraction is found in either eye, the lens(es) must be refit with the indicated change in sphere power. If the indicated lens power is not available for either eye (e.g., outside the available SKU range), the subject will be discontinued (proceed to final evaluation).

2.13	Lens modification (if necessary)	
If modification is necessary in one or both eyes, select the reason for refitting lenses:
 
 • (For toric lenses only) The settled lens rotation is such that a different cylinder axis would be more appropriate (use the LARS rule to determine the replacement lens cylinder axis) • The spherical over-refraction is not plano • Other (specify reason) 
Repeat steps 2.8 through 2.12 for one or both eyes, as appropriate.
 
A maximum of 2 lens modifications are allowed per eye. If, for either eye, the fit is not successful after 2 modifications, the subject will be discontinued (proceed to final evaluation).

2.14	Stop timer for timing contact lens fit	Once a successful lens fit is achieved (no further modifications necessary and plano over-refraction in both eyes), record the stopping time for completing the contact lens fitting procedures.

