122×10^{-11} (cm ² /sec) (ml O ₂ /ml x mm Hg) at 35°C	Fatt (boundary corrected, non-edge corrected)
103×10^{-11} (cm ² /sec) (ml O ₂ /ml x mm Hg) at 35°C	Fatt (boundary corrected, edge corrected)

Lens Parameters:

- Diameter Range: 12.0 mm to 15.0 mm
- Center Thickness: varies with power
- Base Curve Range: 7.85 mm to 10.00 mm
- Spherical Power Range: -20.00D to +20.00D
- Cylinder Power Range: [REDACTED] .25D to -10.00D
- Axis Range: 2.5° to 180°

AVAILABLE LENS PARAMETERS

ACUVUE OASYS® Brand 1-Day with HydraLuxe™ Technology are hemispherical shells of the following dimensions:

Diameter:

14.3 mm

Center Thickness:

0.085 mm to 0.221 mm (varies with power)

Base Curve:

8.5 mm, 9.0 mm

Powers:

-0.50D to -6.00D (in 0.25D increments)

-6.50D to -12.00D (in 0.50D increments)

+0.50D to +6.00D (in 0.25D increments)

+6.50D to +8.00D (in 0.50D increments)

ACUVUE OASYS® Brand 1-Day with HydraLuxe™ Technology for ASTIGMATISM are hemitoric shells of the following dimensions:

Diameter:

14.3 mm

Center Thickness:

0.075 mm to 0.172 mm (varies with power)

Base Curve:

8.5 mm

Powers:

+0.00D to -6.00D (in 0.25D increments)

Cylinders: -0.75D, -1.25D, -1.75D, -2.25D*

Axis: 10° to 180° in 10° increments

*-2.25D cylinder is available in 10°, 20°, 70°, 80°, 90°, 100°, 110°, 160°, 170°, 180° axes only.

+0.25D to +4.00D (in 0.25D increments)

[figure not shown]
-6.50D to -9.00D (in 0.50D increments)

Cylinders: -0.75D, -1.25D, -1.75D

Axis: 10°, 20°, 70°, 80°, 90°, 100°, 110°, 160°, 170°, 180°

TRANSMITTANCE CURVES

ACUVUE OASYS® 1-Day with HydraLuxe™ Technology (senofilcon A)
Visibility Tinted with UV Blocker vs. 24 yr. old human cornea and 25 yr. old
human crystalline lens.

* The data was obtained from measurements taken through the central 3-5 mm portion for the thinnest marketed lens (-9.00D lens, 0.075 mm center thickness).

¹Lerman, S., Radiant Energy and the Eye, MacMillan, New York, 1980, p. 58, figure 2-21

²Waxler, M., Hitchins, V.M., Optical Radiation and Visual Health, CRC Press, Boca Raton, Florida, 1986, p. 19, figure 5

WARNING: UV absorbing contact lenses are NOT substitutes for protective UV absorbing eyewear, such as UV absorbing goggles or sunglasses because they do not completely cover the eye and surrounding area. The patient should continue to use UV absorbing eyewear as directed.

ACTIONS

In its hydrated state, the contact lens, when placed on the cornea, acts as a refracting medium to focus light rays onto the retina.

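### Toric study stock equals the first-fit set exactly, so the refit steps can call for lenses the study does not hold, mainly on the test lens

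*Combined protocol and SAP*

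**What the plan says.** Criterion 8 (Section 3.2) admits refraction cylinder axes "between 165° and 15° (i.e., 180±15°, inclusive) or between 75° and 105° (i.e., 90±15°, inclusive". Criterion 7 requires the spherical equivalent minus half the label cylinder to lie between −0.875 and −4.625 DS inclusive. For first fit, step 2.6 (Section 7.2, Visit 2) says: "Label cylinder axis should be determined by rounding the refraction cylinder axis to the nearest 10 degrees". Axis ties go towards 180 or 90. Sphere ties go to the less minus power.

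Table 1 (Section 6.1) lists toric axes "10, 80, 90, 100, 170, 180", toric spheres of minus "1.00 to -4.50 in 0.25 steps", and control spheres of minus "1.25 through -5.50 (inclusive) in 0.25 steps".

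Step 2.10 treats toric rotation up to 20° as acceptable. Step 2.13 allows a toric refit when another axis would suit better and tells the site to "use the LARS rule to determine the replacement lens cylinder axis". Step 2.12 requires a plano over-refraction with either lens: "If the indicated lens power is not available for either eye (e.g., outside the available SKU range), the subject will be discontinued". Visit 4 repeats these steps. Section 5.1 places randomization before the first fitting, and Section 14.9 rules out imputation.

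Appendix C lists the toric lens, in both study cylinders, from 0.00 to −6.00 D with "Axis: 10° to 180° in 10° increments". It lists the spherical lens from −0.50 to −6.00 D in 0.25 D steps.

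**The concern.** A fitting protocol that permits refits needs stock beyond the first-fit set. Here the toric stock appears to stop exactly where first fit stops, in both axis and sphere. The control needs no axis at all and is stocked past its eligible high-minus limit. If so, supply rather than the product decides some toric outcomes: an off-axis lens is dispensed, or a randomized subject is lost.

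The primary comparison (P1), CLUE vision (S1), the comparison with spectacles (S2) and the exploratory count of diagnostic lenses all depend on how the toric was fitted. With no rule for an unstocked axis, about 12 sites could handle the same eye differently.

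**Working it through.** **1. Axes at first fit.** Rounding the 62 eligible integer axes (165–180, 1–15, 75–105) by step 2.6 gives exactly {10, 80, 90, 100, 170, 180}. This reproduces Table 1 with no spare axis.

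**2. Axes after LARS.** Each of the six labels can shift in two directions, giving 12 pairs.
- A 10° shift is unstocked in 4 of 12: 10→20, 80→70, 100→110, 170→160.
- A 20° shift is unstocked in 8 of 12. The axes called for are 20, 70, 110 and 160 again, plus 30, 60, 120 and 150.

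**3. Toric sphere.** The range −0.875 to −4.625 rounds to labels −1.00 to −4.50, which is the stock. A 0.25 D outward over-refraction therefore calls for −0.75 or −4.75, and neither is held. At exactly −0.875 the tie rule itself gives −0.75.

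**4. Control sphere.** Power needed = toric target + half the label cylinder.
- Cylinder −0.75: −0.875 − 0.375 = −1.25, to −4.625 − 0.375 = −5.00. Against stock of −1.25 to −5.50 this leaves no low-minus spare and two high-minus spares.
- Cylinder −1.25: −0.875 − 0.625 = −1.50, to −4.625 − 0.625 = −5.25. This leaves one spare at each end.

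On a 0.25 D refraction grid with an assumed 12 mm vertex distance, 72 refractions are eligible. A 0.25 D over-refraction in either direction reaches an unstocked power in 9 toric cases and 1 control case. With vertex distances of 0, 13 and 14 mm the counts are 10–11 toric and 1–2 control. These count grid points, not patients.

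**5. Axis frequency (assumed distributions).** The documents give no distribution of refraction axis or lens rotation. Assume normal rotation truncated at ±20°, and axes either normal around 180/90 or uniform over the eligible range. Add rotation to refraction axis and round to 10°. Percentage of eyes needing an unstocked axis:

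| Axis distribution | Rotation SD 3° | 5° | 7.5° |
|---|---|---|---|
| SD 5° | 0.7 | 2.7 | 7.9 |
| SD 8° | about 3 | 6.7 | 12.6 |
| Uniform | about 8 | 12.8 | 18.9 |

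**6. Acuity.** Residual cylinder from misalignment θ is 2·C·sin θ. At 10° this is 2 × 0.75 × 0.174 = 0.26 D, or 2 × 1.25 × 0.174 = 0.43 D, which is 35% of the correction. Table 7 shows a difference of −0.09 − (−0.02) = −0.07 logMAR between toric and sphere in another lens family. Linear scaling (an assumption) gives 0.07 × 0.35 ≈ 0.024 logMAR in an eye misaligned by 10°.

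For the trial mean, count only the excess over a fully stocked set, which would still leave rounding error. In the step 5 model, using the nearest stocked axis, affected eyes are misaligned by 7–10° on average, of which 4–8° is due to stock. Averaged over all eyes, the shift is 0.0001–0.0022 logMAR (normal axes) and at most 0.0035 (uniform axes, rotation SD 7.5°). The worst case is 0.0035/0.025 = 14% of the smaller Table 8 effect and 0.0035/0.05 = 7% of the S2 margin.

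**7. Losses.** The allowance is 170 − 153 = 17 subjects, and 153/0.90 = 170. Paired-t power with SD of difference 0.09·√(2(1 − r)) and effect 0.025 reproduces Table 8 at n = 153: 0.823, 0.876 and 0.927 for r = 0.3, 0.4 and 0.5. If a further 17 were lost (n = 136), power would be 0.776, 0.835 and 0.896.

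**The case against.** Much of the case on the other side stands.

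- Step 2.12 foresees an unavailable power and states the outcome. The sphere limit is therefore a written rule, with about 10% dropout planned and replacement of discontinued subjects allowed (Section 4.3). Replacement restores the count, but not the randomized comparison among those lost.
- A reader might infer that a site must discontinue a subject whose LARS axis is not stocked. The text does not say so. Rotation up to 20° is acceptable under step 2.10, and step 2.17 separately requires 20/40 or better and vision the subject accepts. Either dispensing or discontinuing is inference; what is certain is that no rule is given.
- A reader might set the 0.024 logMAR loss beside the −0.025 in Table 8 and conclude that stock could cancel the planning effect. One is a loss in an affected eye, the other a mean over the whole trial. They are not comparable.
- The control is not exempt: an eye with label cylinder −0.75 that needs −1.25 has no less-minus control lens.
- The −0.875 tie is an edge case. On the 0.25 D grid with 12–14 mm vertex distance, no eligible refraction lands on it.
- Four extra axes do not cover every 20° rotation. Narrowing criterion 8 cannot close the gap either, because label 180 rotated by 20° already calls for 20 or 160.

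**Conclusion.** The gap between Table 1 and steps 2.12–2.13 is certain and follows from the protocol's own rules. It falls mainly on the toric lens. It is a supply choice, since Appendix C shows that the missing parameters are marketed.

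Its practical size is not known. The 1–19% axis range rests wholly on assumed distributions, and the mean effect on HLHC VA is probably small, at most about 0.004 logMAR under the linear scaling.

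A reader might infer a one-way handicap to the test lens. The documents do not support that. Off-axis lenses that are kept work against the toric. Loss of hard-to-fit toric eyes after randomization, without imputation, can favour it. The loss is also uneven by sequence: a toric-first subject lost at Visit 2 contributes no follow-up acuity, while a sphere-first subject lost at Visit 4 contributes control and spectacle acuity but no toric acuity.

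The power tables are not wrong on this account. The matter is worth correcting because the losses are avoidable, concentrated on one lens and cheap to reduce.

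**What to change.** Reconcile Table 1, criteria 7–8 and steps 2.6, 2.12 and 2.13.

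1. Preferably extend the study stock within the Appendix C range: toric spheres −0.75 and −4.75, AO1D −1.00, and toric axes 20, 70, 110 and 160. In the step 5 model this leaves at most 1.8% of eyes needing an unstocked axis.
2. Write one rule for an axis that is still not stocked, applied alike at all sites. Which rule is for the sponsor's clinical team.
3. Record "parameter not stocked" as its own discontinuation reason, and report it by lens and sequence.

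Cost: toric combinations rise from 15 × 6 × 2 = 180 to as many as 17 × 10 × 2 = 340 across about 12 sites, plus an amended Table 1 and one added reason code at Final Evaluation step F.1. No visit, staff or procedure is added.
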